24.0 Blood Draw

24.1 *Will blood be collected specifically for this research?

Yes No

25.0 Blood Draw Details

25.1 *Source of Blood Samples (Check all that apply.)

Subjects as part of a clinical trial
 Blood Donors with a condition or a disease that are NOT part of a clinical trial
 The Scripps Research Institute (TSRI) Normal Blood Donor Service (NBDS)
 OTHER normal blood donors NOT part of the Normal Blood Donor Service (NBDS)

If Other, please explain where the samples are coming from:

(If you are using TSRI NBDS, be sure to include an NBDS Donor Information Form with your submission.)

25.2 *Describe in simple language how this blood will be used.

Blood samples will be used for serum pregnancy test (if female), complete metabolic panel (CMP), that includes gamma glutamyl transferase (GGT), and complete blood count (CBC w/diff) for general bodily functioning. In addition, blood will be drawn for drug concentration and to measure plasma cortisol, aldosterone, and selected cytokines.

25.3 *How frequently will the blood samples be collected?

Less Than 2 Times per Week
 More Than 2 Times per Week
 N/A Outside Scripps

25.4 *How much blood (ml) will be collected each draw?

Less Than 50 Mls (10 teaspoons)
 More Than 50 Mls (10 teaspoons)
 N/A Outside Scripps

25.5 *Who will draw the blood?

[name], our Research Medical Assistant who is a certified phlebotomist, will draw the blood samples.

25.6 If blood will be obtained outside of Scripps, will the samples be obtained with Informed Consent? (Note: If Yes, attach a copy of the IRB approval and/or approved Informed Consent from the other site to the Initial Review Submission Form.)

Yes
 No
 N/A

If No, please explain why:

25.7 *Will the blood be used for genetic analysis?

Yes No

25.8 If Yes, will the results of the genetic analysis be shared with subjects? (REMINDER: If you plan to share the results, consider adding the Genetic Information Nondiscrimination Act language to the consent. Please click on the grey 'Help' button in the upper right to view the genetic language template.)

Yes No

If Yes, explain how the results will be used:

25.9 *Will ALL blood samples used in the study be de-identified?

Yes No

25.10 *Will leftover de-identified blood be used for other studies? (Future plans must first be reviewed by a Scripps IRB.)

Yes No

26.0 Subject Compensation

26.1 *Will subjects receive any payment or compensation for participation in this study?

Yes No

27.0 Subject Compensation Detail

27.1 *Describe all payments/reimbursement being offered to subjects, such as transportation expenses, meals, gifts, and other out-of-pocket expenses.

Subjects will be reimbursed at the following rates: \$50 for the screening visit (Visit 1), \$75 for the randomization visit (Visit 2), \$50 for an interim virtual visit between Visits 2 and 3, \$275 for the cue reactivity visit (Visit 3), and \$50 for the virtual follow-up visit (Visit 4). The total compensation for completion of all 4 study visits is \$500.00.

How will subjects be paid? (Check all that apply.)

- Cash
- Check from investigator, sponsor, CRO, or other outside entity
- Check request or payroll payment through Scripps (requires W-9 tax form)
- Gift certificate
- Through payroll (Scripps Health Employees)
- Scripps Greenhire Card
- Other

If Other, please explain:

27.2 *How much will each subject be paid per visit? And in total?

Subjects will be reimbursed at the following rates: \$50 for the screening visit (Visit 1), \$75 for the randomization visit (Visit 2), \$50 for an interim virtual visit between Visits 2 and 3, \$275 for the cue reactivity visit (Visit 3), and \$50 for the virtual follow-up visit (Visit 4). The total compensation for completion of all 4 study visits is \$500.00.

27.3 *Describe your plan for issuing subject payments: (For example: per visit, end of study, etc.)

Subjects will be paid with a check at the end of each visit that they complete. The payment

following the final, virtual visit will be mailed to the subject following completion of the visit.

27.4 *Will there be any costs (such as prolonged hospitalization, extra tests, co-payments) to subjects associated with their participation in research?

Yes No

If yes, please explain.

27.5 Who will pay for the treatment of a research related injury?

Sponsor
 Subject or his or her medical insurance
 Other
 Not Applicable

If other, describe.

If a subject needs either medical care or urgent medical treatment as a result of their participation in the study, TSRI general liability insurance will cover the costs.

28.0 Study Plan - Details

28.1 Research Methods - Include the Schedule of Events or provide a precise description of the data collection methods. (Attach the Schedule of Events to the Initial Review Submission Form, if applicable)

This is a randomly assigned, double-blind, placebo-controlled outpatient study of the effectiveness of 2-weeks of oral CORT118335 (900 mg/d) for decreasing alcohol cue-induced craving for alcohol in subjects with alcohol use disorder of moderate or greater severity (AUD-MS). Alcohol cue reactivity procedures will be conducted on the last day of dosing (Day 14), with endpoints selected to assess the effects of drug on alcohol cue-induced craving in the lab, as well as on naturalistic measures of protracted abstinence involving sleep, mood, craving and relapse to drinking. A positive signal on such indices would lend support to the potential utility of the drug for the treatment of alcohol use disorder.

Initial Phone Screening

Clinically trained study personnel provide information about the study. Interested individuals who meet initial eligibility criteria are scheduled for a face-to-face intake evaluation.

Visit 1, Screening

After providing written informed consent, subjects complete a Screening Visit for evaluation of eligibility (see Table 1). The Mini-International Neuropsychiatric Interview (MINI; Sheehan & Lecrubier, 2015) for DSM-5 will be administered to determine the inclusion criteria of current AUD with ≥ 4 symptoms and to rule out major psychiatric disorders that would warrant study exclusion. The subject's demographic information, medical and alcohol use history, adverse events and use of concomitant treatments will be recorded using standardized forms. Vital signs and BAC will be assessed, and specimens for urinalysis, serum pregnancy test (if female), urine drug screen, blood chemistry that includes liver function tests (LFTs) and GGT, and complete blood count with differential (CBC w/diff) will be collected by the medical assistant and prepared for same day pick up by LabCorp for analyses. A mini-cue session familiarizes subjects with the cue reactivity lab setting and identifies non- cue-reactive subjects for study exclusion (Visual Analogue Scale [VAS] craving severity rating of alcohol cue ≥ 3 points higher than water cue).

Visit 2, Randomization

Subjects complete the evaluation for eligibility, including ECG, repeat negative pregnancy test and physical exam. Medically cleared subjects complete baseline clinical assessments and are randomized to receive a 2-week supply of double-blind study medication.

Visit 3, Alcohol Cue Session

Subjects return 2 weeks after randomization to complete the alcohol cue session. The alcohol cue session will last for two hours (Table 2).

Table 2. Alcohol Cue Session Procedures

Baseline

1:00 pm: Subject arrives: BAC, vital signs; adverse events and concurrent drug therapy; urine Elg/Ets screen for alcohol and uds for illicit drug use; blood samples obtained; TLFB; CIWA; clinical assessments (i.e., ACQ, PSQI, BDI, STAI).

1:40 pm: Subject prepped for cue session: electrodes attached, and impedance checked; baseline VAS obtained. Subject given instructions and cue-reactivity practice trial.

Cue-Reactivity Trials

2:00 pm: Step 1- Mood induction: subject exposed to block of 12 affective images (pleasant, unpleasant or neutral), psychophysiological recording.

Step 2- In vivo beverage cue: alcohol or water in front of subject for 90 s while recalling picture-induced mood, psychophysiological recording.

Step 3- Ratings: subjects complete VAS craving, and manipulation check in presence of beverage cue.

Step 4- Beverage removed from testing area after completion of ratings.

2:15 pm: Repeat Steps 1-4 for remaining affect-beverage trial combinations (six trials total).

End of Lab Study Procedures

2:45 pm: Debriefing and relaxation period, subject completes ACQ, and BDI-II to verify return to baseline.

Visit 4, Follow-up

Subjects will participate in a scheduled virtual visit 2-weeks after the cue session and discontinuation of study drug to assess persistence of treatment effects and resolution of any adverse reactions. Motivational interviewing and potential treatment options are provided by a study clinician. The study physician conducts a virtual review with all subjects of Week 3 lab results, ECG, status of any adverse events, and at-home Week 4 pregnancy test results with female subjects.

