20.0 Drug Details

20.1 *Are any investigational drugs used in the study?

Yes No

20.2 *List all investigational drugs and active comparator drugs to be used in this study:

View Details	Drug Name	FDA Approved	A new drug or a new use of an already approved drug:	IND Number
	Trade Drug Name: CORT118335			
	Generic Drug Name:	No	Yes	Cross-referencing #142502
	Investigational Drug Name:			
	Trade Drug Name:	CORT118335		
	Generic Drug Name:			
	Investigational Drug Name:			
	Is the drug supplied at no cost?	Yes		
	Is the Drug FDA Approved:	No		
	Is this a new drug or a new use of an already approved drug	Yes		
	Is an IND necessary	Yes		

IND Number:	Cross-referencing #142502
Who holds the IND:	PT holds the IND
IND details:	Please see the Letter of Authorization (attached to this submission) from Corcept allowing [name] to cross-reference their IND for this study. [name] will hold the Investigator-initiated IND for this project.
If FDA Approved and an IND is not required, Please provide a rationale for exemption:	
Dose Range:	900 mg
Frequency:	1x per day for 14 days
Route of administration:	Orally
Will the Investigational pharmacy be dispensing?	No
Identify who will be preparing the investigational drug /biologic for administration and describe in detail how it will be prepared:	CORT118335 150 mg tablets and matched placebo tablets will be provided by Corcept Therapeutics. The daily dose of six 150 mg tablets will be packaged in wallet cards provided by Corcept Therapeutics that contains a 2-week supply of double-blind medication, plus a 1-week extra supply for rescheduling purposes if needed.
Indication(s) under Investigation:	Alcohol Use Disorder (AUD)
Where will the drug be stored	Scripps Research, Laboratory of Clinical Psychopharmacology
Drug Storage Restrictions (including temperature, etc.):	Room Temperature
Administration Instructions:	900 mg (6 tablets) my mouth each morning with food
Possible Untoward Effects, Their Symptoms & Treatment:	
Excessive glucocorticoid or mineralocorticoid receptor antagonism symptoms:
 
 Unusual tiredness or weakness Nausea and/or vomiting Dizziness when standing Aches and pains Loss of appetite or weight loss Dehydration Diarrhea Feeling depressed 
Participants reporting symptoms of excessive glucocorticoid or mineralocorticoid receptor antagonism during treatment will be discontinued from the study drug and seen promptly for medical evaluation

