Contraindications and Interactions, If Known:	Chronic systemic steroid use and use of and drugs that are strong inhibitors and inducers of CYP2C9 will be exclusionary.

20.3 *Describe your plan for storing, dispensing and accounting for the study drug(s).

The medication is stored in a locked cabinet in the medication room that is kept locked at the Laboratory of Clinical Psychopharmacology. Our pharmacy technician will prepare and label a box containing a 2-week supply of double-blind medication (CORT118335 and placebo), plus a 1-week extra supply for rescheduling purposes if needed. They will also keep the randomization code and maintain record of study medication dispensed and returned throughout the study. The Study Coordinator or Clinical Research Assistant will monitor medication compliance by recording the number of pills dispensed at randomization (Visit 2) and returned at the cue session (Visit 3) on a drug dispensation case report form.

20.4 *Name all persons who will dispense the study drug(s) and sign drug accountability records.

[name]
[name]
[name]

20.5 *Has the investigational pharmacy been notified?

Yes
 No

If Not, please explain:

(N/A)

20.6

Check all drugs that will be paid for by the sponsor or study budget.

Investigational Drugs
 Other Study Drugs (including placebo)

20.7 If applicable, offer a proposed mechanism of action for investigational drugs or approved drugs under study for a new indication:

Glucocorticoid receptor (GR)/ mineralocorticoid receptor antagonist

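### The PSQI at the Day 14 visit has no recall window tied to dosing; with a recall of about one month, roughly 50–58% of the recalled nights would precede the first dose on schedule

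*Protocol*

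**What the plan says.** Protocol section 28.1 says the endpoints were chosen to show drug effects on cue-induced craving and on "naturalistic measures of protracted abstinence involving sleep, mood, craving and relapse to drinking". Sleep also appears in the primary hypothesis (section 29.1) and in the anticipated benefits (section 34.8).

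The sleep instrument appears once, in the Baseline block of Table 2 for Visit 3: "clinical assessments (i.e., ACQ, PSQI, BDI, STAI". No recall period, version or scoring rule accompanies it.

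On timing, "Alcohol cue reactivity procedures will be conducted on the last day of dosing (Day 14") and "Subjects return 2 weeks after randomization to complete the alcohol cue session". Section 20.2 gives the frequency as "1x per day for 14 days" and the instruction as "900 mg (6 tablets) my mouth each morning with food". The supply is two weeks "plus a 1-week extra supply for rescheduling purposes if needed", so Visit 3 can slip.

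At Visit 2, section 28.1 refers to baseline clinical assessments without listing them. The virtual follow-up takes place "2-weeks after the cue session and discontinuation of study drug to assess persistence of treatment effects", again without a list of scales. The SAP names drinks per day from the Timeline Followback as the naturalistic outcome and does not mention sleep or the PSQI.

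**The concern.** The quantity of interest is sleep during the two weeks on drug. A questionnaire completed at the end of those two weeks measures it only if its recall is no longer than the time on drug. With a longer window, the Visit 3 score averages untreated and treated nights, and it also overlaps the period that a Visit 2 score would describe.

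At stake is the ability to see a sleep effect in a proof-of-concept study that plans 50 subjects and is looking for a positive signal. A diluted score makes a null result hard to interpret: it could mean no effect on sleep, or that many of the nights scored were untreated.

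**Working it through.** The documents give no recall window, no share of nights and no power for sleep, so there is no stated figure to reproduce.

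**Inputs**
- Nights on drug, T. Morning dosing from Day 1 and a 1:00 pm arrival on Day 14 give T = 13. Two full weeks after randomization give T = 14. A delay of the full reserve week gives T = 20–21.
- Recall, R. Not in the documents. Assumed 28–31 nights for about one month, with 14 and 21 for comparison.
- Sample size: 50 subjects (section 37.5); 25 per arm assumes equal allocation.

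**Share of recalled nights before the first dose** = max(0, R − T) / R

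| T | R=14 | R=21 | R=28 | R=30 | R=31 |
|---|---|---|---|---|---|
| 13 | 7.1% | 38.1% | 53.6% | 56.7% | 58.1% |
| 14 | 0% | 33.3% | 50.0% | 53.3% | 54.8% |
| 16 | 0% | 23.8% | 42.9% | 46.7% | 48.4% |
| 20 | 0% | 4.8% | 28.6% | 33.3% | 35.5% |
| 21 | 0% | 0% | 25.0% | 30.0% | 32.3% |

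For example, 15/28 = 53.6% and 18/31 = 58.1%.

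**Power, simplest model.** Take a true effect of 0.8 SD, a two-sided 5% t-test and 25 per arm. The score responds in proportion to nights on drug and its SD does not change, so the effect becomes 0.8 × T/R.
- Recall matched to dosing: 79%.
- R = 28: T/R = 0.464–0.500, power 25–28%.
- R = 30: T/R = 0.433–0.467, power 23–25%.
- R = 31 with T = 13: T/R = 0.419, power about 21%.
- Full-week delay, R = 28–30: T/R = 0.667–0.750, power 46–55%.

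**Power, letting the SD change (R = 28, T = 14).** Give each fortnight's sleep variance 1, with equal correlation ρ between fortnights (0 to 0.7) and instrument-noise variance ν (0 to 0.5).
- The 14-day score has variance 1 + ν, so an effect of 0.8 SD is 0.8√(1+ν).
- The one-month score averages two fortnights. Its effect is half of that and its variance is (1+ρ)/2 + ν.
- Its standardised effect is therefore 0.4√(1+ν) / √((1+ρ)/2 + ν). At ρ = 0, ν = 0 this is 0.566, power 50%. At ρ = 0.7, ν = 0.5 it is 0.422, power 31%. The unadjusted range is thus 31–50%, against 79% with 14-day recall.
- With the baseline score as covariate, divide each standardised effect by √(1 − r²). For 14-day recall r = ρ/(1+ν). For one-month recall r = [(1+3ρ)/4] / [(1+ρ)/2 + ν].
- Adjusted power is then about 41–96% with one-month recall, against 79–97% with 14-day recall. At the favourable extreme (ρ = 0.7, ν = 0) the two are nearly equal, 96% against 97%. At ρ = 0.7, ν = 0.5 they are 43% and 88%.

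**The case against.** The strongest objection is that the size of the problem rests on a recall period the documents do not state. With a 14-day recall there is essentially no defect. Table 1 is cited but is not in the available text, the Visit 2 battery is not itemised and the questionnaire forms are not reproduced, so a shorter recall could be specified there. This stands as a limit: the documents establish that no window is tied to dosing, and the percentages are conditional.

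A reader might infer that more than half of the scored nights are untreated for every subject. The documents do not support that. Even with one-month recall the share is exactly half at 28 nights with 14 on drug, and it drops below half once the visit falls about 16 nights after the first dose, which the reserve supply permits.

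A reader might also infer that a real sleep effect would probably be reported as absent. That follows only from the fixed-SD, unadjusted model. Averaging over a longer window also reduces the SD, and the overlap with baseline makes the covariate more predictive, so adjusted power can stay high. A loss remains in most scenarios, but its size depends on correlations and noise that the documents do not give. Equal weighting of recalled nights is a further simplification.

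Finally, the consequences are contained. The SAP's first-listed comparison is the cue-session VAS score, and no PSQI analysis is specified. This reduces the priority. It does not remove the point, because sleep is part of the stated hypothesis.

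**Conclusion.** The point holds as a cheap improvement. The protocol treats sleep as an expected drug effect, measures it at Visit 3 with the only sleep scale in the available text, and does not limit recall to the dosing period. Any recall longer than the time on drug counts untreated nights as treatment nights.

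For an assumed recall of 28–31 nights, the pre-drug share is about 50–58% on schedule and about 25–36% after a full-week delay. For a true 0.8 SD effect with 25 per arm, power falls from 79% to about 23–50% unadjusted (R = 28–30, visit on schedule), and the loss is usually smaller with baseline adjustment.

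Two further readings should be resisted. Pre-drug nights enter both randomized arms alike, so the comparison is pulled toward zero and does not favour drug. It might also be inferred that a follow-up PSQI would fail to show persistence, but nothing in the text says the scale is given at that visit.

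**What to change.** State in Table 2 and in the Visit 2 assessment list that the PSQI is answered for the past two weeks at both visits. Apply the same instruction at the virtual follow-up only if the scale is given there. The baseline and on-drug windows then overlap by at most about one night, and the Visit 3 window stays within dosing even if that visit is delayed.

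Add a sentence to the SAP: compare Visit 3 PSQI scores between arms with the Visit 2 score, if collected, as covariate.

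For data already collected with a longer recall, report that the window includes pre-drug nights and do not read a null result as no effect on sleep.

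The cost is one line of questionnaire instruction and the matching protocol wording, with no added visit, scale or staff. The downside is that two-week scores are less directly comparable with published scores from the standard form.

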29.0 Study Plan - Clinical Trial

29.1 Clinical Trial Details

*Describe the design of the study (double blind, randomized, etc.)
(Enter N/A if not applicable.)

Double-blind, random assignment

*Describe any preliminary data that supports or refutes the hypothesis to be tested.

Our study is based on positive studies of mifepristone, a mixed glucocorticoid receptor (GR) antagonist and progesterone antagonist, in preclinical and human laboratory models of AUD (Vendruscolo et al., 2015) and a recently completed clinical trial of mifepristone in 103 outpatients with AUD (IND # 114497, NCT02179749). This project also builds on positive preclinical studies of the GR/mineralocorticoid receptor (MR) antagonist, CORT118335, in rodent models of AUD, that found CORT118335 significantly reduced alcohol self-administration without affecting water self-administration or the consumption of a non-alcoholic saccharin-sweetened solution, indicating that CORT118335 did not suppress consummatory behaviors in general.

*Describe previous research, pre-clinical or clinical findings that led to the proposed research. (In early phases of drug or device development where there is little human data, provide the type and number of patients who have received the drug, device or procedure to date.)

The theoretical rationale for GR/MR as novel targets for reducing craving in AUD is based on the neurobiology of abstinence in AUD which involves activation of brain stress systems, which CORT118335 is hypothesized to normalize. This stress response is initiated by activation of the hypothalamic-pituitary-adrenal (HPA) axis, leading to increases in glucocorticoid release. Glucocorticoids bind to GR and mediate adaptation to stress and regulate termination of the glucocorticoid stress response through negative feedback at the level of the HPA axis. Chronic stress, AUD, and the consequent impaired GR feedback have been proposed to lead to the dysregulation of HPA axis activity. Additionally, activation of GR drives MR activation of other stress-related neuropeptides, e.g., corticotropin releasing factor and norepinephrine, thereby further contributing to increasing stress, anxiety and compulsive-like ethanol drinking (Vendruscolo et al., 2012). Thus the activity of CORT118335 as a GR/MR antagonist may have significant therapeutic potential for AUD. A key rationale for the study of modulators of the brain emotional systems in AUD treatment is that medications that normalize the dysregulation or balance of the reward and stress systems may protect against relapse during protracted abstinence. For example, acute withdrawal and protracted abstinence from alcohol is associated with not only decreased dopaminergic function but also increased extrahypothalamic corticotrophin releasing factor function which is driven by GR. The GR is also involved in mediating inflammation, which has been identified as a potential treatment target for AUD; an ancillary benefit of CORT118335 may be a reduction in several inflammatory cytokines and chemokines that may be upregulated in AUD (e.g., TNF-alpha, IL-1, IL-2, IL-6, and chemokines CCL2 and CCL19) and have a positive feedback to reactivate and perpetrate a dysregulated HPA axis.

The primary hypothesis under test is that treatment with CORT118335, a GR/MR antagonist that modulates the activity of cortisol and aldosterone, will result in significant improvements in subjective craving following alcohol-cue exposure in the lab and in naturalistic measures of protracted abstinence that include relapse to drinking, craving and disturbances in sleep and mood. Support for this hypothesis is provided by pre-clinical and clinical studies of GR and MR antagonists in AUD. Preclinical studies of the GR antagonist, mifepristone, showed reduced alcohol intake in alcohol-dependent rats, but not in non dependent animals, and a double-blind study of 56 non treatment-seeking alcohol dependent subjects showed 1-week of treatment with mifepristone 600mg/d significantly reduced alcohol craving and consumption compared to placebo in the above human lab model (Vendruscolo et al., 2015). We recently completed a randomized, double-blind trial of 1-week of mifepristone 1200 mg/d, 600 mg/d or matched placebo followed by 8-weeks of counseling in 103 treatment-seeking outpatients with AUD. Preliminary analyses replicated the earlier effects of mifepristone found in the lab model involving non treatment seekers with AUD, i.e., significantly decreased drinking for the week on drug and for the following 2 weeks in individuals who did not have abstinence as a treatment goal. Effectiveness in this group was linearly related to mifepristone plasma level, with equivalent efficacy in men and women. Consistent with the half-life of the drug, effects were not detected after 2 weeks post treatment. Individuals who entered treatment with abstinence as a treatment goal did well with counseling, regardless of whether their assigned drug was mifepristone or placebo. Mifepristone significantly ($p < 0.05$) improved ALT and GGT relative to placebo. Taken together, the preclinical, human lab model and clinical trial results lend support to the therapeutic potential of GR antagonism as a treatment strategy for AUD.

¹A relationship between the aldosterone-MR pathway and alcohol drinking also has been found in studies across 3 species: rats, monkeys and humans (Aoun et al., 2018). Of note, non-abstinent AUD patients had significantly higher circulating aldosterone levels than abstinent AUD patients, and aldosterone levels were positively correlated with the quantity of alcohol consumed, as well as with craving and anxiety scores.

Spironolactone is an aldosterone/MR antagonist that has been shown to significantly reduce alcohol self-administration in rodent models of AUD, and an analysis of data from patients with AUD from the Veteran Birth Cohort, found those treated with spironolactone (for any reason, n=10,726) showed a significant reduction in Alcohol Use Disorders Identification Test-Consumption (AUDIT-C) score, relative to AUD patients not treated with spironolactone (Farokhnia et al., RSA 2020, attached with permission).

*Describe and justify any withdrawal of standard medications or the inclusion of a placebo.

Withdrawal of standard medications will not be allowed for inclusion into the study. Rather, if subjects are taking medications that are exclusionary, then they will not be allowed to participate

in the study.

A placebo group is necessary in order to effectively evaluate the effects of the target medication.

